2.1 Study Objectives

2.1.1 Primary Objective

• To determine the effectiveness of IMPACT in reducing CAS

2.1.2 Key Secondary Objective

• To determine the effectiveness of IMPACT in reducing stimulant use

2.1.3 Secondary Objective

• To determine the effectiveness of IMPACT by format of intervention (in-person vs. virtual)

2.1.4 Non-Clinical Implementation Objective

• To evaluate the multifaceted implementation strategy in terms of adoption and accessibility, implementation, maintenance, and dissemination including cost-effectiveness of IMPACT

2.2 Study Endpoints

2.2.1 Primary Endpoint

• Distinct acts of CAS defined as anal sex acts without the use of a condom or without the protection of prevention-effective PrEP (for participants NLWHIV) or viral suppression (for participants LWHIV) over the course of study follow-up

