	 Access to a computer/smartphone/tablet that can use video chat (e.g., Zoom or Google Meet); Provide a mailing address where they can receive a package; Access to stable internet that they can use for more than 2 hours at a time; Have a private place (where no one else can see or hear) where they can complete visits online; and Reside within the continental United States (U.S.).
Main Criteria for Exclusion	 Unable to provide informed consent due to severe mental or physical illness; Concurrent enrollment in another HIV prevention or treatment study (enrollment in a substance treatment program is acceptable); Non–English-speaking; Is currently incarcerated or pending incarceration; or Any other medical condition, medical/behavioral intervention, or other condition that, in the opinion of the SC Project Lead or designee, could interfere with the safety of participants or staff, adherence to study procedures, or compromise interpretation of study results.
Clinical Centers	Five SCs in the U.S. will participate in this study. Participants may also participate virtually through centralized administration of online assessments and video-based intervention sessions.
Study Duration	Estimated duration: 5 years
Length of Participation	Total participant duration: Approximately 12 months

Study Intervention	IMPACT is a status-neutral intervention that uses behavioral activation (BA)—an evidence-based, cognitive behavior therapy—as a treatment for stimulant use and sexual risk reduction (RR) counseling for YGBSMM.
	The IMPACT intervention includes 10 sessions: 2 intervention sessions of HIV RR, 1 session focused on orienting and rationale of BA, 6 sessions integrating BA and RR—including pre-exposure prophylaxis (PrEP) or antiretroviral therapy (ART) and HIV care—and 1 final session on relapse prevention.
	The enhanced Standard of Care (eSOC) group includes two HIV RR intervention sessions.
Criteria for Evaluation	 Primary endpoint: Distinct acts of CAS defined as anal sex acts without the use of a condom or without the protection of prevention-effective PrEP (for participants not living with HIV [NLWHIV]) or viral suppression (for participants living with HIV [LWHIV]) over the course of study follow-up
	 Key secondary endpoint: Stimulant use over the course of study follow-up (based on urine drug testing via Point-of-Care Testing [POCT] and/or self-report)

PROTOCOL SCHEMA

Figure 1 Flow Diagram of Study

Version 3.0 Version Date: 03-October-2024

1. Introduction

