1.2.2.3 NIDA-Funded Pilot RCT of the IMPACT Intervention

In this pilot RCT, 41 participants NLWHIV (21 intervention, 20 control) were randomized across the two study arms: (1) BA-RR (BA and RR counseling), which lasted 10 sessions, and (2) the eSOC comparison arm, which included 2 equivalent RR counseling sessions without any additional intervention.^[13] Participants were followed for 6 months. Main outcomes included the number of CAS acts without protection of PrEP and the number of stimulant use episodes. At

baseline, in the prior month, participants had an average of 11 sexual partners, had CAS 18 times on average, and had CAS while using stimulants 16 times on average. In longitudinal Poisson regression models, the main sexual risk outcome data showed fewer CAS acts overall between the intervention and comparison arm (p<0.0001). Similarly, fewer CAS acts were demonstrated while using stimulants (2.24 [0.2] vs. 6.94 [0.4] p<0.0001) and fewer CAS acts with a serodiscordant partner while using stimulants (1.0 [0.2] vs. 2.5 [0.4] p=0.0005), both at 6-month follow-up. Also, at 6-month follow-up, the intervention group reported a longer period of stimulant non-use in the past 90 days (50.10 [1.5] vs. 39.00 [1.4] p<0.0001] vs. standard of care (SOC)).

1.2.2.4 National Institute of Allergy and Infectious Diseases/Centers for AIDS Research Funded Pilot of IMPACT Intervention for MSM with HIV

An open pilot trial of the IMPACT intervention (approximately 10 BA sessions) was conducted for MSM with stimulant use disorder who were LWHIV (n=11).^[12] This study provides preliminary evidence that the intervention for this population was feasible (100% retention at 6 months) and acceptable (100% of intervention sessions attended). Exit interviews indicated that the intervention was well received and acceptable. The mean change score in self-reported stimulant use within the past 30 days (within-person change; reduction in self-reported stimulant use) was 4.14 days at 3 months and 5.0 days at 6 months (Cohen's d=0.89). The mean change score in weekly toxicology screens (reduction in positive toxicology screens) was .71 at 3 months and 1.0 at 6 months (Cohen's d=1.05).

2. **Objectives and Endpoints**

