Participants will be followed for 1 year, with assessments at enrollment and Months 4, 8, and 12. Figure 1 (Flow Diagram of Study) provides a schematic of the study. At each time point, participants will provide a urine sample and a blood sample, and complete a self-report psychosocial and sexual risk assessment battery. Primary outcomes include the number of CAS acts while not protected by PrEP (YGBSMM NLWHIV) or while not virally suppressed (YGBSMM LWHIV) and stimulant use. We will also test our multifaceted implementation strategy by assessing adoption/accessibility and implementation using mixed-methods assessments that describe and examine characteristics of successful implementation (including differences by intervention delivery format). Finally, we will assess the feasibility of maintenance and sustainment of Project IMPACT by using the well-established CEPAC-AYA model to project its cost-effectiveness on HIV transmissions, quality-adjusted life years, and perperson lifetime costs.

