3.1.1 Rationale for Study Endpoints

When conducting research on HIV prevention and treatment, it is essential to include study endpoints that capture relevant sexual risk behaviors and their relationship to preventive measures such as condom use, PrEP, and viral suppression. The rationale for incorporating a study endpoint that asks about CAS acts and whether they are protected by PrEP (for individuals NLWHIV) and/or viral suppression (for individuals LWHIV) includes:

- 1. **HIV transmission risk.** CAS is a high-risk behavior for HIV transmission. Understanding its occurrence and the level of protection provided by preventive measures is crucial for evaluating the effectiveness of the IMPACT intervention. By incorporating this study endpoint, we will collect data on actual anal sex acts and be able to determine the risk of transmission associated with CAS with and without the protection of PrEP/viral suppression.
- 2. **Monitoring progress.** Incorporating this study endpoint enables us to determine intervention effectiveness in reducing CAS acts and improving the level of protection provided by PrEP and viral suppression over time. Thus, it allows us to assess the effectiveness of the IMPACT intervention on improving additional HIV prevention approaches beyond condom use over study follow-up. For example, monitoring progress allows us to assess whether the IMPACT intervention improves PrEP adherence or ART adherence (viral suppression) in the context of ongoing CAS acts over the course of 12 months.
- 3. **Tailoring IMPACT intervention sessions.** For individuals NLWHIV, if CAS is not protected by PrEP, we initiate a conversation about either (1) PrEP uptake or (2) a need for enhanced adherence support or education. For individuals LWHIV, if CAS occurs without viral suppression, we initiate a conversation about either (1) initiating HIV treatment or (2) enhanced adherence support or education. As such, this endpoint allows for tailored IMPACT intervention sessions based on individual risk profiles.

Using a study endpoint that asks about CAS acts and their protection by PrEP (for individuals NLWHIV) and/or viral suppression (for individuals LWHIV) provides a comprehensive, real-world understanding of sexual risk among the participant population over study follow-up.

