14.2 Sample Size Considerations

Careful consideration was given to the effect size used in the power analysis and is estimated based on data from previous studies. In our pilot study, the mean difference in CAS acts between the intervention versus control arm at 6 months was 4.7 (>50% reduction). Although the pilot study had a large effect on reductions in sexual risk behaviors, effect sizes from small studies like the pilot study are less reliable and frequently inflated.^[70] Additionally, in the present study, the eSOC comparison group will be receiving two RR sessions and, as such, they will likely also decrease their engagement in CAS. Therefore, the study is powered to detect a 20 percent (or greater) reduction in the number of CAS acts between groups in the 12-month follow-up period, expecting both groups to show improvements from baseline. This decision will account for the fact that in clinical trials in general, and HIV behavioral trials in particular, when the control group receives any of the intervention content, it is more difficult to find a between-group difference^[71-73] as well as take into account the fact that the primary timeframe in the present study is 12 months instead of 6. Lastly, a 20 percent or greater reduction in the number of CAS acts has been previously described as a clinically meaningful change related to HIV sexual risk outcomes.

Moreover, to ensure sufficient power to assess whether intervention effectiveness differs between intervention delivery format (i.e., virtual vs. in-person) with a power of 90 percent, alpha level of 0.05, 291 participants will need to complete the proposed intervention in order to examine difference between IMPACT (n=194) and eSOC control (n=97). We plan to randomize 360 participants (n=240 in IMPACT and n=120 in eSOC) to account for 20 percent attrition at the month 12 visit.

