14.3.3 Analysis of Primary Endpoint

Estimands

The primary analysis of the primary endpoint will compare the rate of distinct acts of CAS over the course of follow-up between the IMPACT intervention arm and the eSOC comparison arm.

For this endpoint, the primary estimand is defined by the following attributes:

- **Intervention condition:** IMPACT intervention versus eSOC including the effects of intervention discontinuation and intake of additional interventions/therapies.
- **Population:** Cisgender YGBSMM as defined by the inclusion criteria to reflect the key population.
- Variable: Number of distinct acts of CAS without the use of a condom or without the protection of prevention-effective PrEP (for participants NLWHIV) or viral suppression (for participants LWHIV) over the course of follow-up.
- Intercurrent events: The following intercurrent events are anticipated:

- Discontinuation of intervention due to any reason
 - Handling strategy: treatment policy (captured through the intervention condition definition)
- Intake of additional interventions/therapies
 - Handling strategy: treatment policy (captured through the intervention condition definition)

Further intercurrent events are not anticipated at this time.

• **Population-level summary:** Rate ratio between intervention conditions

Analysis Models

For the primary endpoint, a marginal Poisson model will be used, with logarithmic link function, common intercept, linear fixed effect for intervention, and accounting for the length of the reporting period for each observation. A Generalized Estimating Equations (GEE) approach will be used to fit the model, assuming an unstructured working correlation structure. Given the possibility of missing data from participants who discontinue the study prior to the Month 12 visit, inverse probability weighting will be incorporated into the modeling procedure; more details will be described in the SAP. Substitute model specifications to be used in the event the primary model does not converge will be described in the SAP.

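### The primary endpoint and estimand join no condom and no PrEP or viral suppression with 'or', while Section 3 requires both, so the protocol defines its primary count in incompatible ways

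*Protocol*

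**What the plan says.** Four places in the protocol define the primary outcome.

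- **Synopsis, Criteria for Evaluation:** "Distinct acts of CAS defined as anal sex acts without the use of a condom or without the protection of prevention-effective PrEP", or viral suppression for participants living with HIV.
- **2.2.1 Primary Endpoint:** the same words, "anal sex acts without the use of a condom or without the protection of prevention-effective PrEP".
- **14.3.3, estimand variable:** "Number of distinct acts of CAS without the use of a condom or without the protection of prevention-effective PrEP", or viral suppression.
- **Section 3, Study Design:** the primary outcomes include "the number of CAS acts while not protected by PrEP (YGBSMM NLWHIV) or while not virally suppressed (YGBSMM LWHIV").

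Two other places bear on what is meant. The pilot RCT summary in 1.2.2.3 says "Main outcomes included the number of CAS acts without protection of PrEP". The endpoint rationale in 3.1.1 says the endpoint should show effectiveness in "improving additional HIV prevention approaches beyond condom use over study follow-up", and should let the team "assess whether the IMPACT intervention improves PrEP adherence or ART adherence (viral suppression) in the context of ongoing CAS acts".

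**The concern.** The first three places use a true disjunction. Because the word for absence is repeated before each clause, either condition is enough for an act to count. Section 3 requires both: the act must be condomless and must also lack PrEP protection or viral suppression.

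These definitions count different acts, and the primary test is a rate ratio of those counts. Under the literal estimand, a participant who starts effective PrEP or becomes virally suppressed while still having condomless sex contributes exactly the same count as before. Yet 3.1.1 gives that kind of benefit as a reason for choosing the endpoint. The PrEP and viral load measurements that 7.5 makes part of primary efficacy would also have no effect on the count.

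This cannot simply be left to the SAP. The protocol itself fixes the endpoint and the estimand, and the opening of Section 14 says that major analysis changes, with a primary endpoint as its example, should come through a protocol amendment. A SAP that followed Section 3 would depart from the estimand as written, and one that followed the estimand would contradict Section 3.

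**Working it through.** **Step 1. Which acts count under each text.** CAS is condomless anal sex (List of Abbreviations).

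| Type of act | Synopsis and 2.2.1, literal | 14.3.3, literal | Section 3 |
|---|---|---|---|
| No condom, not covered | counts | counts | counts |
| No condom, covered by PrEP or suppression | counts | counts | does not count |
| Condom, not covered | counts | does not count | does not count |
| Condom, covered | does not count | does not count | does not count |

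The synopsis and 2.2.1 start from all anal sex acts, so the literal text also admits condom-protected acts by participants without biomedical protection. That contradicts the label CAS. The estimand in 14.3.3 starts from acts of CAS, which are already condomless, so its protection clause has no effect and every CAS act counts. Taken literally, there are three definitions.

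**Step 2. Inputs.** The only design figure available is the 20% reduction in 14.2, a rate ratio of 0.80. The protocol gives no condom use and no PrEP or suppression coverage, so these are assumed:

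- c0, c1 = share of acts covered in eSOC and IMPACT. c0 is set at 0.20, 0.30 and 0.50.
- k = share of acts with a condom, set at 0.1, 0.3 and 0.5, equal in both arms and independent of coverage.
- Both arms have the same number of anal sex acts.

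**Step 3. The intervention works through coverage.**

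- Section 3: RR = (1 − c1)/(1 − c0). Setting RR = 0.80 gives c1 = 1 − 0.8(1 − c0), that is 0.36, 0.44 and 0.60, or gains of 16, 14 and 10 percentage points.
- 14.3.3, literal: all CAS acts count, so RR = 1.00.
- Synopsis and 2.2.1, literal: everything counts except condom plus coverage, so RR = (1 − k·c1)/(1 − k·c0).

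| c0 → c1 | Section 3 | 14.3.3, literal | 2.2.1, k = 0.1 | 2.2.1, k = 0.3 | 2.2.1, k = 0.5 |
|---|---|---|---|---|---|
| 0.20 → 0.36 | 0.80 | 1.00 | 0.984 | 0.949 | 0.911 |
| 0.30 → 0.44 | 0.80 | 1.00 | 0.986 | 0.954 | 0.918 |
| 0.50 → 0.60 | 0.80 | 1.00 | 0.989 | 0.965 | 0.933 |

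**Step 4. The opposite direction.** Suppose CAS falls by 40%, but only among covered participants, who account for c0 of eSOC CAS acts.

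- 14.3.3, literal: RR = (1 − c0) + 0.6·c0 = 0.92, 0.88 and 0.80 for c0 = 0.20, 0.30 and 0.50.
- Section 3: the uncovered acts are unchanged, so RR = 1.00.

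**Step 5. The pilot figure in 14.2.** 14.2 says "the mean difference in CAS acts between the intervention versus control arm at 6 months was 4.7", a reduction of more than 50%. Section 1.2.2.3 reports 6-month means of 2.24 and 6.94: 6.94 − 2.24 = 4.70, and 4.70/6.94 = 67.7%. The figure reproduces, but 1.2.2.3 reports those means for CAS acts while using stimulants, which is none of the definitions above.

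**The case against.** The strongest reply is that the intent can be recovered. Section 7.5 bases primary efficacy on a self-reported count of CAS over the past 4 months combined with PrEP adherence samples, injection records and viral load. The literal 2.2.1 reading would also need a count of condom-protected acts, which 7.5 does not mention, and the literal 14.3.3 reading would leave the biomarkers idle. Only Section 3 fits. This stands as evidence of intent, but 7.5 does not state how the count and the biomarkers are combined. It supports correcting the text; it does not make the text correct.

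A second reply is that support for the Section 3 reading is not uniform. The objective (2.1.1), the hypotheses (14.1) and the 20% target (14.2) speak of CAS with no mention of protection, and one item in 3.1.1 refers to risk both with and without it. Those uses can rest on a defined term, but only once that term is defined in one way. They are also a reason for the sponsor to confirm the meaning.

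Third, the illustration is constructed: coverage in the IMPACT arm is solved to give 0.80, and the 1.00 follows from assuming equal acts and condom use. That is true. It shows that the definitions can diverge and in which directions, not by how much they will.

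Fourth, 14.4 summarizes PrEP and ART use and adherence by arm, so gains there would still be reported. They would not enter the primary test.

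**Conclusion.** The point holds. The synopsis, 2.2.1 and the estimand in 14.3.3 define the primary count by a disjunction, Section 3 defines it by a conjunction, and no text reconciles them. Under the stated assumptions, an effect that meets the 20% target under Section 3 appears as 1.00 under the literal estimand and as 0.91 to 0.99 under the literal 2.2.1 text. An effect confined to covered participants appears as 0.80 to 0.92 under the literal estimand and as 1.00 under Section 3. The actual size cannot be known from the protocol. This should be corrected before analysis, because it determines which acts the primary test counts.

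**What to change.** In the synopsis, 2.2.1 and the estimand variable in 14.3.3, change the connective between the condom clause and the protection clause from *or* to *and*. An act then counts only if it was condomless and also lacked prevention-effective PrEP (participants not living with HIV) or viral suppression (participants living with HIV). The sponsor should confirm that Section 3 is the intended meaning. The objective, hypotheses and secondary endpoints can keep the term CAS as defined.

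In 14.2, add a clause naming the outcome behind the pilot difference of 4.7, and do not relabel it with the corrected endpoint term. The sponsor should also confirm that the 20% target refers to the corrected endpoint. The 291 completers cannot be re-derived under any of the definitions, because 14.2 gives no event rate, dispersion or within-person correlation.

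The cost is one word in three places and one clause in 14.2, made by protocol amendment. No new data collection is needed.

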2.2.2 Key Secondary Endpoint

• Stimulant use over the course of study follow-up (based on urine drug testing via POCT and/or self-report)

2.2.3 Secondary Endpoints

- Distinct acts of CAS by intervention format
- Stimulant use by intervention format

2.2.4 Non-Clinical Implementation Endpoints

- Adoption and Accessibility*
 - Intervention uptake and completion rates by participant demographics, intervention format, site characteristics, and interventionist background
 - Client Satisfaction Questionnaire (CSQ)-8 scale scores and intervention satisfaction rates
 - *Satisfaction* is defined a priori by achieving standardized scores of 80 percent or greater on the CSQ-8 scale.^[74]

*The following implementation measures are approved as an exempt component of this research: interventionist knowledge, self-efficacy, and skills pre- and post-training, by format, site, and timepoint

- Maintenance
 - Structured qualitative interview of individuals responsible for conducting the IMPACT intervention at each site
 - Coding of a select subset of participant and staff qualitative interview transcripts to identify themes related to intervention implementation and dissemination
 - Incremental cost-effectiveness of IMPACT versus eSOC estimated using the Cost Effectiveness of Preventing AIDS Complications for Adolescents and Young Adults (CEPAC-AYA) model

3. Study Design

We will use the RE-AIM Framework to inform the design, implementation, and evaluation of the IMPACT intervention to reduce stimulant use and concurrent HIV sexual transmission risk. Following best practices described in the Expert Recommendations for Implementing Change (ERIC) framework,^[17] we will use a multifaceted training and implementation strategy for the Project IMPACT intervention across sites and formats (see details below). We will then enroll approximately 450 YGBSMM who report stimulant use in the context of CAS, who will be randomized using a 2:1 allocation ratio to either the IMPACT intervention or an eSOC control. Allowing for drop out prior to randomization, we aim to randomize 360 YGBSMM. To ensure geographic variability in our sample, we will enroll nationally. Those physically located near a participate in-person, while those not located near an ATN SC will participate virtually (i.e., online assessments and video-based counseling). We anticipate that about 50 percent of the randomized sample will participate virtually (n=180) and 50 percent inperson (n=180), and randomization will be stratified by site and format; the study is well-powered to detect differences in intervention effectiveness by format.

Participants will be followed for 1 year, with assessments at enrollment and Months 4, 8, and 12. Figure 1 (Flow Diagram of Study) provides a schematic of the study. At each time point, participants will provide a urine sample and a blood sample, and complete a self-report psychosocial and sexual risk assessment battery. Primary outcomes include the number of CAS acts while not protected by PrEP (YGBSMM NLWHIV) or while not virally suppressed (YGBSMM LWHIV) and stimulant use. We will also test our multifaceted implementation strategy by assessing adoption/accessibility and implementation using mixed-methods assessments that describe and examine characteristics of successful implementation (including differences by intervention delivery format). Finally, we will assess the feasibility of maintenance and sustainment of Project IMPACT by using the well-established CEPAC-AYA model to project its cost-effectiveness on HIV transmissions, quality-adjusted life years, and perperson lifetime costs.

